5.3 Flowchart of the study cohort assembly

For zoledronic acid vs. raloxifene

	Optı	ım CDM	IBM® Ma	rketScan®
	Excluded Patients	Remaining Patients	Excluded Patients	Remaining Patients
All patients		77,673,639		200,203,908

	-77,476,067	197,572	-	489,107
Did not meet cohort entry criteria			199,714,801	
Excluded due to insufficient enrollment	-52,317	145,255	-164,242	324,865
Excluded due to prior use of referent	-81,791	63,464	-185,458	139,407
Excluded due to prior use of exposure	-9,268	54,196	-29,153	110,254
Excluded because patient qualified in >1 exposure category	-1	54,195	-1	110,253
Excluded based on Inclusion #1 - Age, range 65-89 years	-17,914	36,281	-58,739	51,514
Excluded based on Inclusion #2 - Gender, female [Excluded if Male or Unknown]	-6,080	30,201	-6,857	44,657
Excluded based on Inclusion #3 - Osteoporosis	-3,624	26,577	-3,936	40,721
Excluded based on Exclusion #1 - Oral bisphosphonate use	-6,854	19,723	-10,259	30,462
Excluded based on Exclusion #2.1 - PTH or PTH analogue use	-305	19,418	-814	29,648
Excluded based on Exclusion #2.2 - Anabolic–androgenic steroids (AAS) and	-10	19,408	-32	29,616
growth hormones (GH)				
Excluded based on Exclusion #2.3 - Glucocorticoids use	-1,352	18,056	-1,697	27,919
Excluded based on Exclusion #3 - CCI (180 days) >=10	-196	17,860	-154	27,765
Excluded based on Exclusion #4 - Malignant neoplasm, excluding non-melanoma	-2,461	15,399	-4,141	23,624
skin cancer				
Excluded based on Exclusion #5 - Disorders that influence bone metabolism	-1,426	13,973	-2,235	21,389
Excluded based on Exclusion #6 - Glucocorticoid-Induced Osteoporosis	-4	13,969	-5	21,384
Excluded based on Exclusion #7 - Paget's Disease	-43	13,926	-65	21,319
Excluded based on Exclusion #8 - Alcohol abuse or Drug addiction or Non-	-141	13,785	-137	21,182
compliance	1	10.504	2	21 170
Excluded based on Exclusion #9 - Pregnancy	-1	13,784	-3	21,179
Excluded based on Exclusion #10 - Lower extremity amputation	-18	13,766	-37	21,142
Excluded based on Exclusion #11 - Denosumab use	-53	13,713	-35	21,107
Excluded based on Exclusion #12 - Zoledronic Acid use (for raloxifene users)	-223	13,490	-313	20,794
Excluded based on Exclusion criteria #13 - End-stage renal disease	-5	13,485	-12	20,782
Excluded based on Exclusion criteria #14 - End-stage liver disease	-33	13,452	-66	20,716
Excluded based on Exclusion criteria #15 - Blindness or low vision	-32	13,420	-25	20,691
Excluded based on Exclusion criteria #16 - Abaloparatide	-0	13,420	-0	20,691

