	Exposure: Zoledronic acid (5 mg) 15-minute intravenous administration every year for 3 years vs. placebo Reference: Placebo Aim: To evaluate the effect of annual infusions of zoledronic acid on fracture risk during a 3-year period in postmenopausal women with osteoporosis All patients received oral daily calcium (1000 to 1500 mg) and vitamin D (400 to 1200 IU).	Exposure: new-use of Zoledronic acid (washout 450 days) NDC Generic Name: ZOLEDRONIC ACID ZOLEDRONIC ACID IN MANNITOL & WATER FOR INJECTION ZOLEDRONIC ACID IN MANNITOL AND 0.9 % SODIUM CHLORIDE ZOLEDRONIC ACID IN MANNITOL AND WATER FOR INJECTION ZOLEDRONIC ACID IN MANNITOL AND WATER FOR INJECTION NDC codes: 143964201, 16729024231, 17478032705, 25021080167, 42023015101, 43598033011, 47335003540, 47333096241, 54288010001, 5511106850755150026605, 67457039054, 68001036625, 78035084, 78038725, 409421501, 409421505, 16714081501, 17478032745, 23155017031, 25021080166, 45963044055, 51991006598, 53150087101, 60505611000, 63232096198, 68001036622, 78043561, 78059061, 409422801, 43598033111, 51991006498, 55111068852, 63323096600, 67457061910, 67457079410, 70860021051 CPT/HCPCS Procedure Codes: C9115, 13487, 13488, 13489, Q2051, Q4095 Reference of primary analysis: Raloxifene (proxy of placebo) Reference of primary analysis: Raloxifene (proxy of placebo)		Criteria	
	PRIMARY	DUTCOME		Adequate mapping in claims	
	Hip fracture (Dual-energy x-ray absorptiometry of the hip was performed at baseline and at months 6, 12, 24, and 36 for bone loss) - both patients in stratum 1 and stratum 2	Measured 1 day after drug initiation (codes reported in "Hip and femur fractures codes": Hip and femur fractures Algorithm include the following case-qualifying (CO): CQ = 1 Inpatient claim with primary diagnosis code AND CQ = 2 Inpatient claim with secondary diagnosis code AND CQ = 3 Non-inpatient claim with diagnosis code AND HCPCS in (27125, 27130, 27220, 27222, 27226-27228, 27230-27248, 27254, 27254, 27267-27269, 27500-27514) OR Non-inpatient claim with diagnosis code AND ICD-9 Procedure Code in (7855, 7905, 7915, 7925, 7935, 7965, 8151, 8152)	Wright NC, Daigle SG, Melton ME, Delzell ES, Balasubramanian A, Curtis JR. The Design and Validation of a New Algorithm to Identify Incident Fractures in Administrative Claims Data J. Bone Miner Res. 2019 Oct;34(10):1798-1807. doi: 10.1002/jbmr.3807. Epub 2019 Aug 5. PMID: 31170317.	Intermediate mapping in claims	

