2	Bone mineral density T score of -2.5 or less at the femoral neck, with or without evidence of existing vertebral fracture, or a T score of -1.5 or less, with radiologic evidence of at least two mild vertebral fractures or one moderate vertebral fracture.	Measured time of enrollment to prior to the day of drug initiation inpatient (any position), outpatient (any position): Osteoporosis diagnosis ICD-9 diagnosis: 733.00, 733.01, 733.02, 733.03, 733.09, 733.13 ICD-10 diagnosis: M81.0, M81.6, M81.8, M80.88*, M80.08* OR Measured time of enrollment to 730 days (2 years) prior to the day of drug initiation: Alendronate, Ibandronate, Risedronate, Pamidronate, Etidronate, Tiludronate		Adequate mapping in claims of criteria extracted from clinicaltrial.gov (ESLD and Svere eye disease), after clinical review with FDA (Abaloparatide, Romosozumab) or from the protocol of Horizon-recurrent (all other criteria in blue): "Colôn-Emeric CS, Caminis J, Suh TT, Pieper CF, Janning C, Magaziner J, Adachi J, Rosario-Jansen T, Mesenbrink P, Horowitz ZD, Lyles KW; HORIZON Recurrent Fracture Trial. The PHORIZON Recurrent Fracture Trial: the prevention of subsequent fractures after low trauma hip fracture repair. Curr Med Res Opin. 2004 Jun;20(6):903-10. doi: 10.1185/03079904125003683. PMID: 15200749." Protocol of Horizon-pivotal not available - numerous unsuccessful attempts had been made to retrive it from the authors	

	EXCLUSION	CRITERIA	
1	Bisphosphonate users such as Aredia® (pamidronate), Didronel® (etidronate), Fosamax® (alendronate), Actonel® (risedronate), Skelid® (tiludronate)	Measured 730 days (2 years) prior to the day of drug initiation: Generic names: Alendronate, Ibandronate, Risedronate, Pamidronate, Etidronate, Tiludronate	
2.1	Previous use of: (1) any previous use of parathyroid hormone	Measured 730 days (2 years) prior to the day of drug initiation: Generic names: Brand names: Natpara® (parathyroid hormone), Forteo®, Bonsity (teriparatide), Tymlos® (abaloparatide)	

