2.2	(2) use of anabolic steroids or growth hormone within 6 months before trial entry	Measured 180 days prior to the day of drug initiation: AASs: Generic names: TESTOSTERONE, DIHYDROTESTOSTERONE PROPIONATE, ESTROGENS, ESTERIFED/METHYLTESTOSTERONE, TESTOSTERONE CYPIONATE, MICRONIZED, TESTOSTERONE CYPIONATE ESTERADIOL CYPIONATE, TESTOSTERONE ENANTHATE-ESTRADIOL OVALERATE, TESTOSTERONE MICRONIZED, TESTOSTERONE UNDEC ANOATE, METHYLTESTOSTERONE, MICRONIZED, STANOLONE, OXYMETHOLONE, NANDROLONE PIENPROPIONATE, OXANDROLONE, STANOZOLO, FLUDXYMESTERONE, TESTOSTERONE ENANTHATE, TESTOSTERONE PROPIONATE, NANDROLONE DECANOATE, METHYLTESTOSTERONE, TESTOSTERONE CYPIONATE GHS: Generic names: SOMATROPIN, TESAMORELIN ACETATE Brand names: OMNITROPE, SAIZEN, ZOMACTON, GEREF, HUMATROPE, NUTROPIN, SEROSTIM, ZORBTIVE, EGRIFTA, MACRILEN, NORDITROPIN FLEXPRO, GENOTROPIN, TEVEROPIN	
2.3	OR (3) oral or intravenous systemic corticosteroids within 12 months,	Measured 30 days prior to the day of drug initiation: Injectable (IV) or (IM): NDC Generic Name: methylprednisolone, hydrocortisone, dexamethasone CPT/HCPCS Procedure Code: J1020, J1030, J1040, J1720, J2920, J2930 Oral: NDC Generic Name: Cortisone, hydrocortisone, prednisone, prednisolone, methylprednisolone, dexamethasone CPT/HCPCS Procedure Code: J7506, J7509, J7510, J8540	
2.4	OR (4) any previous use of strontium, or sodium fluoride within 6 months before trial entry	CRITERIA NOT APPLIED	Strontium not approved in USA for treatment of osteoprosis. Sodium Fluoride is not used to treat the osteoporosis since 2001/2002 when a RCT and sub meta-analysis showed an increased of risk of fractures in the exp
NA	Patients with a serum calcium level of more than 2.75 mmol per liter or less than 2.00 mmol per liter	N/A	
NA	Patients with a calculated creatinine clearance of less than 30.0 ml per minute at either of two baseline visits or urine dipstick results of more than 2+ for protein, without evidence of contamination or bacteriuria.	N/A	
NA	Written informed consent	N/A	
3	Serious disease that may limit life expectancy to less than 6 months (including sever liver and renal diseases)	Measured 180 days prior to the day of drug initiation: CCI >=10 (life expectancy less than the expected duration of the trial)	

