13	End-Stage Renal Disease	Measured 180 days prior to and including day of drug initiation in any diagnosis position and inpatient or outpatient care setting: 2 codes for occurrence of ESRD/dialysis (either inpatient or outpatient), separated by at least 30 days: ICD-9 Diagnosis: S85.6, V45.1, V56.0, V56.8, 585.5 ICD-9 Procedure: 39.95, 54.98 ICD-10 Diagnosis: N18.5, N18.6, Z49.31, Z49.32, Z99.2 ICD-10 Procedure: 39.95, 54.98 ICD-10 Procedure: 3EIM392, SA1D60Z, SA1D00Z, 3EIM39Z, SA1D60Z, 5A1D00Z ICD-10 Procedure: 3EIM39Z, SA1D60Z, 5A1D00Z, 3EIM39Z, SA1D60Z, 5A1D00Z ICD-10 Procedure: 3EIM39Z, SA1D60Z, S01D00Z, 3EIM39Z, SA1D60Z, 5A1D00Z ICD-10 Procedure: 3EIM39Z, SA1D60Z, S01D00Z, 3EIM39Z, SA1D60Z, SA1D00Z ICD-10 Procedure: 3EIM39Z, SA1D60Z, S01D00Z, S	Patorno, Elisabetta et al. "Cardiovascular outcomes associated with canagifilozian vicrus other non-giffilozian atidabetic drugs: population based cohort study." BMJ 2018;360:k119 http://dx.doi.org/10.1136/bmj.k119 Patorno, Elisabetta et al. "Empagifilozia and the Risk of Heart Failure Hospitalization in Routine Clinical Care: A First Analysis from the Empagifilozia Comparative Effectiveness and Safety (EMPRISE) Study." Circulation. 2019 Apr 8. doi: 10.1161/CIRCULATIONAH.118.039177
		OR Kidney transplant: ICD-9 Diagnosis: 996.81, V42.0 ICD-9 Procedure: 55.6, 55.69 ICD-10 Diagnosis: 786.10, T86.13, T86.19, Z48.22, Z94.0, T86.11, T86.12 ICD-10 Procedure: 0T700Z0, 0T700Z2, 0TY10Z0, 0TY00Z1, 0TY10Z1, 0TY10Z2 WICDS-CPT_Code-S0366 , S0365	
14	End-Stage Liver Disease	Measured 180 days prior to and including day of drug initiation in any diagnosis position and inpatient or outpatient care setting: Cirrhosis. ICD-9 Diagnosis: 571.2, 571.5, 571.6 ICD-10 Diagnosis: K70.11, K70.2, K70.3x, K70.4x, K74.x Hepatic decompensation: ICD-9 Diagnosis: 456.0, 456.20, 456.1, 456.21, 789.5, 789.59, 572.2, 567.0, 567.2, 567.21, 567.22, 567.29, 567.8, 567.89, 567.89, 567.9, 572.4 ICD-10 Diagnosis: R18.x, 185.x, K72.x, K65.x, K66.x, K67 HCC is already excluded with exclusion criteria 4	
15	Blindness or compromised vision	Measured 180 days prior to and including day of drug initiation in any diagnosis position and inpatient or outpatient care setting: ICD-9 Diagnosis: 369.x ICD-10 Diagnosis: H54.x	
16	Abaloparatide	Measured 450 (1 year +90 days) prior to the day of drug initiation: Generic name: Abaloparatide	
17	Romosozumab	Measured 450 (1 year + 90 days) prior to the day of drug initiation: Generic name: Romosozumab	

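### Exclusion 1 is any bisphosphonate in the design diagram and Appendix A but oral bisphosphonate in the flowchart, and as printed it has no procedure codes to find an infusion billed only as a procedure

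*Protocol*

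**What the plan says.** The protocol states the criterion in three places.

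- **Section 4, design diagram (Figure 1).** Prior use of a bisphosphonate or parathyroid hormone is excluded over days -730 to 0. No route is given.
- **Appendix A, exclusion row 1.** The trial criterion is given as "Bisphosphonate users such as Aredia® (pamidronate), Didronel® (etidronate), Fosamax® (alendronate" and further brands. The implementation column reads "Measured 730 days (2 years) prior to the day of drug initiation: Generic names: Alendronate, Ibandronate, Risedronate, Pamidronate, Etidronate, Tiludronate". It names no route and no procedure codes.
- **Section 5.3, flowchart.** The step is reported as "Excluded based on Exclusion #1 - Oral bisphosphonate use". It removes 6,854 women in Optum and 10,259 in MarketScan.

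Section 5.2.2 says that the definitions are given in Appendix A and summarised in the flowchart, so the two should agree.

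Elsewhere Appendix A pairs drug names with procedure codes. The zoledronic acid exposure has NDC names, NDC codes and CPT/HCPCS codes. Exclusion 2.3 has "Injectable (IV) or (IM): NDC Generic Name: methylprednisolone, hydrocortisone, dexamethasone CPT/HCPCS Procedure Code: J1020, J1030, J1040, J1720, J2920, J2930", and it lists procedure codes for the oral corticosteroids as well.

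**The concern.** The labels describe different cohorts. If the flowchart label is literal, the cohort departs from the protocol's own criterion. If Appendix A was run as printed, the label is wrong, and the criterion still depends on a drug name appearing in the record.

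The protocol looks for its own infused study drug through procedure codes as well as drug names, so it does not rely on names alone to find infusions. An earlier infusion of another bisphosphonate that was billed only by procedure code would pass the name search.

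The comparison is between an infused bisphosphonate and a proxy for placebo, and this step exists to remove recent exposure to the same class. A woman who has already had infusions may be more likely to move to another infusion than to a daily tablet. Missed users could therefore gather in the zoledronic acid arm.

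**Working it through.** **1. The plan's own counts reproduce.**

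| | Optum | MarketScan |
|---|---|---|
| Reaching Exclusion 1 | 26,577 | 40,721 |
| Removed | 6,854 | 10,259 |
| Remaining (computed) | 19,723 | 30,462 |
| Remaining (Section 5.3) | 19,723 | 30,462 |
| Share removed | 6,854/26,577 = 25.8% | 10,259/40,721 = 25.2% |

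The next largest numbered exclusion (Exclusion 4, malignancy) removes 2,461 and 4,141. The criterion with the conflicting label is thus the one that shapes the cohort most.

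**2. Scope, side by side.**

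| Place | Route | How found |
|---|---|---|
| Section 4 diagram | not limited | not stated |
| Appendix A, row 1 | not limited | six generic names |
| Section 5.3 flowchart | oral | not stated |
| Appendix A, zoledronic acid | infusion | names, NDC and procedure codes |
| Appendix A, row 2.3 | IV, IM and oral | names and procedure codes |

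A record carrying a listed name is caught if Appendix A was run as written. A record with only a procedure code is not. The protocol does not state the route of pamidronate or ibandronate; I take it as an assumption that some of this use is by infusion or injection.

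**3. What the recorded history shows.** Appendix B, Table 1 has a row for prior bisphosphonate use. In the matched table the row label is displaced, and I identify the row by its order.

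- Before matching (raloxifene vs zoledronic acid): Optum 1,625/6,815 = 23.8% vs 1,597/6,605 = 24.2%; MarketScan 2,397/6,694 = 35.8% vs 5,368/13,997 = 38.4%.
- After matching, pooled: 2,825/9,014 = 31.3% vs 3,093/9,014 = 34.3%.
- Standardised difference = (p1 - p2)/√[(p1(1-p1) + p2(1-p2))/2] = -0.063 from the counts. The printed -0.0639 follows from the rounded percentages.

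Recorded use is slightly commoner in the zoledronic acid arm. The row does not separate oral from infused use, so it says nothing about infusions that the search missed.

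**4. Possible size, by assumption only.** Let a share m of the zoledronic acid arm be missed users with hazard r relative to the other women in that arm, and let the raloxifene arm have none. Then approximately HR(observed) = HR(true) × (1 - m + m·r). Neither m nor r is in the protocol. I take r from 0.6 to 1.5.

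| HR(true), Section 1.6 | m = 1% | m = 5% |
|---|---|---|
| 0.59 (3 years) | 0.588 to 0.593 | 0.578 to 0.605 |
| 0.745 (18 months) | 0.742 to 0.749 | 0.730 to 0.764 |

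For example, 0.59 × (0.95 + 0.05 × 0.6) = 0.578 and 0.59 × (0.95 + 0.05 × 1.5) = 0.605. The sign depends on r.

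**The case against.** The strongest reply is that the printed appendix is not the full implementation. It sends the reader to an external drive for further detail or missing information. Its denosumab row shows no drug name or code, yet the flowchart removes 53 and 35 women at that step. Raloxifene has no codes printed, yet 6,815 + 6,694 = 13,509 users were assembled. Nor is the use of procedure codes uniform: the rows for parathyroid hormone, anabolic steroids, abaloparatide and romosozumab show names only. This stands. The absence of printed codes does not prove that none were searched, and a flowchart label is a summary, not the executed query. But the stated reason for moving lists to the drive is cell size and the number of ICD-10 codes. That does not readily explain leaving out a few procedure codes when others are printed in the same table. The conflict of scope remains in any case.

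Four stronger readings are tempting, and the documents do not support them.

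- **That infused users were in fact left in.** This follows only for infusions billed solely by procedure code, and only if the external list lacks those codes.
- **That the leak is one-sided.** It is plausible, but there is no count by route or arm.
- **That a missed woman is also recorded as having no prior bisphosphonate use, so Table 1 hides the problem.** The covariate is not defined in the protocol. It is positive in 24% to 38% of women after a 730-day exclusion, so it is not the same variable as Exclusion 1.
- **That the number missed can be scaled from the number removed.** No share by route is given. A count at this step would also overstate the final number, because only 34,111 of the 50,185 women left after Exclusion 1 (68%) reach the final cohort.

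The zero removals for romosozumab ("Generic name: Romosozumab") are not evidence of missed users either. They may reflect true absence; abaloparatide also removes none, having been covered already by Exclusion 2.1.

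**Conclusion.** The point holds as an inconsistency with a possible gap in capture. The protocol states one exclusion with two scopes. As printed, the definition does not find a bisphosphonate infusion billed only by procedure code, although the same appendix lists procedure codes for other infused or injected drugs. It affects the largest numbered exclusion, about a quarter of the women reaching it in each database, in a comparison where the exposure belongs to the excluded class.

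The bias cannot be computed from the protocol in size or direction. It is probably modest: at 5% contamination of one arm, with the relative hazard between 0.6 and 1.5, the hazard ratio moves by at most 0.019 on either starting value. That range rests on assumed inputs. The conclusion also assumes that the external code list, which is not available here, does not already settle the matter. It is worth correcting because the correction is small and the date of the comparative analysis (Section 13) is still blank.

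**What to change.** 1. Reconcile the flowchart label in Section 5.3 with Appendix A row 1 and the Section 4 diagram, so that all three state the same scope.
2. State whether procedure codes for infused or injected bisphosphonates were searched. Unless the external list already contains them, add those for pamidronate and ibandronate to Exclusion 1 and print them in Appendix A.
3. Define the prior bisphosphonate use covariate (window and codes) and check that it uses the same code set.
4. Report the additional women excluded, by arm and database, then re-run the matching, Table 1 and the Section 10 power figures before any comparative result is produced.

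The cost is a few codes, one re-run and a small loss of patients. MarketScan has 13,997 zoledronic acid users against 6,694 raloxifene users, so many losses there could be replaced. Even without replacement the effect on power is slight. With the Section 10 pooled 187.49 events, Φ(√(events/4) × |ln HR| - 1.96) reproduces the stated 0.951 at a hazard ratio of 0.59. With 5% fewer events (178.1) it is 0.941. At the 18-month value of 0.745 the corresponding figures are 0.522 and 0.502.

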6.3.1 Outcome variables

Effectiveness outcome variables of interest (definitions provided in **Appendix A**):

Primary outcome: Hip fracture

- Secondary outcome:
 - o Non-vertebral fracture

6.3.2 Study follow-up

Intention-to-treat (ITT) analysis will be conducted with treatment defined as the index drug on day of cohort entry. Because the exposure (zoledronic acid) is administered annually, patients receiving the exposure are automatically covered with medication for at least 12 months. In addition, the comparator (raloxifene) is intended to proxy for placebo, so nonadherence to the comparator does not result in meaningful exposure misclassification. Therefore, the ITT analysis with a follow-up of 18 months (540 days) will be the primary analysis.

The follow-up will start the day after drug initiation (i.e., cohort entry date), as described in the HORIZON-PFT, and will continue until the earliest date of the following events:

- The first occurrence of the outcome of interest,
- The date of end of continuous registration in the database,
- End of the study period,
- Measured death event occurs,
- Nursing home admission
 - Nursing home admissions are considered a censoring event because the data sources utilized typically provide little to no data on a
 patient, particularly on drug utilization, after admission. We will utilize this as an exclusion reason for cohorts for the same
 reason.

7. Initial Feasibility Analysis

Action report name:

For zoledronic acid vs. raloxifene

Optum CDM- https://bwh-dope.aetion.com/projects/details/1406/results/60058/result/0 IBM® MarketScan®- https://bwh-dope.aetion.com/projects/details/1406/results/60058/result/0

Date conducted: 10/17/2020

Complete Action feasibility analysis using age and CCI as the only covariates and the primary endpoint (Section 6.3.1) as the outcome. No measures of association will be computed nor will incidence rates stratified by treatment group.

• Report patient characteristics by treatment group

• For zoledronic acid vs. raloxifene

		Optum CDM		IBM® MarketScan®		
Variable	Raloxifene - Comparator	Zoledronic Acid - Exposure	Difference	Raloxifene - Reference	Zoledronic acid - Exposure	Difference
Number of patients	6,815	6,605	-	6,694	13,997	-
Age						
mean (sd)	73.41 (5.90)	74.02 (5.52)	-0.62 (-0.81, - 0.42)	73.81 (7.06)	75.61 (7.14)	-1.80 (-2.01, - 1.60)
median [IQR]	73.00 [68.00, 78.00]	75.00 [69.00, 79.00]	-	72.00 [68.00, 79.00]	75.00 [70.00, 81.00]	-
Combined Comorbidity Score - CCI (180 days)						
mean (sd)	1.38 (1.52)	1.49 (1.56)	-0.11 (-0.16, - 0.06)	0.96 (1.20)	1.22 (1.35)	-0.27 (-0.30, - 0.23)
median [IQR]	1.00 [0.00, 2.00]	1.00 [0.00, 2.00]	-	1.00 [0.00, 1.00]	1.00 [0.00, 2.00]	-

- Report summary parameters of study population FEASIBILITY- FOR STUDY OUTCOME
 For zoledronic acid vs. raloxifene

	Optum CDM	IBM® MarketScan®
Number of patients in full cohort	13,420	20,691
Number of patients dropped as incomplete cases	0	0
Number of patients that did not begin follow-up	0	0
Number of patients in analytic cohort	13,420	20,691
Number of events	146	208
Number of person-years	16,243	24,519
Number of patients in group: Raloxifene - Comparator	6,815	6,694
Number of patients in group: Zoledronic Acid - Exposure	6,605	13,997
Risk per 1,000 patients	10.88	10.05
Rate per 1,000 person-years	-	-

- Report median follow-up time by treatment group
 For zoledronic acid vs. raloxifene

Median Follow-Up Time (Days) [IQR] – ITT analysis					
Patient Group Optum CDM IBM® MarketScan®					
Overall Patient Population	540 [375, 540]	540 [340, 540]			
Referent - Raloxifene	540 [363, 540]	540 [363, 540]			
Exposure - ZA	540 [383, 540]	540 [329, 540]			

- Report reasons for censoring in the overall study population
 For zoledronic acid vs. raloxifene

Reasons	Optum CDM	IBM® MarketScan®
Overall	10750	17260
Outcome	146 (1.1%)	208 (1.0%)
Death	0 (0.0%)	62 (0.3%)
Maximum follow-up time	8,891 (66.3%)	13,112 (63.4%)
End of patient data	0 (0.0%)	0 (0.0%)
End of patient enrollment	2,589 (19.3%)	5,969 (28.8%)
Nursing home Occurred	838 (6.2%)	630 (3.0%)

• Report overall risk of the primary outcome.

	Optum CDM	IBM® MarketScan®	Pooled
Risk per 1,000 patients	10.9	10.1	10.4

8. Initial Power Assessment

Action report name:

For zoledronic acid vs. raloxifene

Optum CDM- https://bwh-dope.aetion.com/projects/details/1406/results/60059/result/0

IBM® MarketScan®- https://bwh-dope.aetion.com/projects/details/1407/results/60061/result/0

Date conducted: 10/17/2020

In order to complete the initial power analysis, the dummy outcome of a 90-day gap in database enrollment will be used. This outcome is used to ensure that no information on the comparative risks of the outcomes of interest are available at this stage. Complete a 1:1 PS-matched comparative analysis using this outcome. PS should include only 2 covariates: age and combined comorbidity index. Power calculations are based on the formulas from Chow et al. (2008).

• Stop analyses until feasibility and power are reviewed by primary investigators and FDA. Reviewers evaluate the results of the analyses described above in Sections 7 and 8, including numbers of patients, patient characteristics, follow-up time, and reasons for censoring by treatment group, as well as overall rates of outcomes and study power. These parameters are re-evaluated and reported in the subsequent sections, after incorporating feedback and refining the protocol.

o Pooled

o Pooled	1
Superiority Analysis	
Number of patients matched	25,518
Reference	12,759
Exposed	12,759
Risk per 1,000 patients	10.40
Desired HR from RCT	0.59
Alpha (2-sided)	0.05
Number of events expected	265.3872
Power	0.990300973

o Optum CDM

Companie vite Amelouie	
Superiority Analysis	
Number of patients matched	12,130
Reference	6,065
Exposed	6,065
Risk per 1,000 patients	10.90
Desired HR from RCT	0.59
Alpha (2-sided)	0.05
Number of events expected	132.217
Power	0.858487133

o IBM® MarketScan®

Superiority Analysis	
Number of patients matched	13,388
Reference	6,694
Exposed	6,694
Risk per 1,000 patients	10.10
Desired HR from RCT	0.59
Alpha (2-sided)	0.05
Number of events expected	135.2188
Power	0.86602361

• Stop analyses until feasibility and power are reviewed by primary investigators, FDA, and assigned members of advisory board.

Reviewed by PI:	[name]	Date reviewed:	10/29/20
Reviewed by FDA:	[name]	Date reviewed:	11/15/20
Reasons for stopping			
analysis (if required):			

9. Balance Assessment

Action report name:

For zoledronic acid vs. raloxifene

Optum CDM: https://bwh-dope.aetion.com/projects/details/1406/results/64560/result/0

IBM® MarketScan®: https://bwh-dope.aetion.com/projects/details/1407/results/64559/result/0

Date conducted: 01/19/2021

After review of initial feasibility and power analyses, complete creation of the remaining covariates from Section 6.2. Again, using the dummy outcome of a 90-day gap in database enrollment, complete a 1:1 PS-matched analysis. The PS should include the complete list of covariates.

• Provide plot of PS distributions stratified by treatment group.

Note- Please refer to Appendix B.

• Report covariate balance after matching.

Note- For Table 1, please refer to **Appendix B**.

• Report reasons for censoring by treatment group.

	Overall	Referent	Exposure
Dummy outcome	697 (3.87%)	350 (3.88%)	347 (3.85%)
Death	89 (0.49%)	36 (0.40%)	53 (0.59%)
End of index exposure	762 (4.23%)	372 (4.13%)	390 (4.33%)
Maximum follow-up time	11993 (66.52%)	6058 (67.21%)	5935 (65.84%)
End of patient enrollment	4487 (24.89%)	2198 (24.38%)	2289 (25.39%)

• Report follow-up time by treatment group.

Median Follow-Up Time (Days) [IQR] – ITT analysis				
Patient Group Optum CDM IBM® MarketScan®				
Overall Patient Population	540 [404.5, 540]	540 [365, 540]		
Referent - Raloxifene	540 [426, 540]	540 [365, 540]		
Exposure - ZA	540 [386, 540]	540 [364.5, 540]		

• Report overall risk of the primary outcome.

	Optum CDM	IBM® MarketScan®	Pooled
Risk per 1,000 patients	10.9	10.1	10.4

10. Final Power Assessment

Date conducted: 01/19/2021

• Re-calculate power in the appropriate excel table, using the revised number of matched patients from the PS-match in Section 9. All other parameters in the table should be the same as in Section 8.

o Pooled

18,028
9,014
9,014
10.40
0.59
0.05
187.4912
0.950774073

o Optum CDM

Superiority Analysis	
Number of patients matched	6,396
Reference	3,198
Exposed	3,198
Risk per 1,000 patients	10.90
Desired HR from RCT	0.59
Alpha (2-sided)	0.05
Number of events expected	69.7164
Power	0.595938014

o IBM® MarketScan®

O IBIVIO IVIGINOUS CALLO				
Superiority Analysis				
Number of patients matched	11,632			
Reference	5,816			
Exposed	5,816			
Risk per 1,000 patients	10.10			
Desired HR from RCT	0.59			
Alpha (2-sided)	0.05			
Number of events expected	117.4832			
Power	0.815816276			

• Stop analyses until balance and final power assessment are reviewed by primary investigators, FDA, and assigned members of advisory board.

Reviewed by PI:	[name]	Date reviewed:	01/19/21
Reviewed by FDA:	[name]	Date reviewed:	01/19/21
Reasons for stopping			
analysis (if required):			

11. Study Confidence and Concerns

Deadline for voting on study confidence and listing concerns:

Date votes and concerns are summarized:

- If final feasibility and power analyses are reviewed and approved, proceed to the remaining protocol steps.
- All study team and advisory board members that review this protocol should at this stage provide their level of confidence for the success of the RWD study in the Google Form. This form also provides space for reviewers to list any concerns that they feel may contribute to a failure to replicate the findings of the RCT, including differences in study populations, poor measurement of study variables, or residual confounding.

All responses will be kept confidential and individual-level results will only be shared with the individual respondent.

• After the deadline for voting has passed, provide the distribution of responses and summarize all concerns here.

12. Register study protocol on clinicalTrials.gov

Date conducted:

• Register the study on clinicalTrials.gov and upload this document.

13. Comparative Analyses

Action report name:

Date conducted:

13.1 For primary analysis:

In the PS-matched cohort from Section 9, to estimate the risk of hip fracture for zoledronic acid users versus raloxifene users during an 18-month period using a Cox regression hazard regression model.

13.2For sensitivity analyses:

Secondary analyses:

- In the PS-matched cohort from Section 9, to estimate the risk of non-vertebral fracture for zoledronic acid users versus raloxifene users during an 18-month period using a Cox regression hazard regression model.
- To estimate the risk of hip fracture for zoledronic acid versus non-user comparator using a risk-set sampled cohort.

Subgroup analysis: In the PS-matched cohort from Section 9, to estimate the risk of hip fracture stratified by age (women younger or older than 75 years). The estimates are compared with the results from a post-hoc analysis of the Horizon-PFT on women older than or equal to 75 (Boonen et al.).

14. Requested Results

